Inclusion Criteria: 1) Eligible for VHA care (information obtained from review of medical record), 2) Age 18-89 (information obtained from review of medical record), 3) Has been deployed to a warzone (information obtained from Veteran self-report/screening interview), 4) Has experienced a morally injurious event which continues to interfere with functioning (information obtained from Moral Injury Events Scale [MIES], Moral Injury Questionnaire-Military Version [MIQ-M], and self-report/screening interview), and 5) Willing to be randomized and participate in either of the two conditions (information obtained from Veteran self-report/screening interview). 6) When groups are only being offered through videoconferencing, participants will need a computer/smartphone capable of accessing the VA approved videoconferencing platform in a private setting.

Exclusion Criteria: 1) Inability to demonstrate understanding of the postcard consent (as evidenced by inability to respond correctly to postcard consent questions or medical record review), 2) Inability to complete study measures (e.g., due to significant acute intoxication/withdrawal symptoms, mania, psychosis, aggression, catatonia, cognitive impairment) (results of veteran self-report, screening, or discretion of interviewer), 3) Imminent suicide risk (medical record or UWRAP), 4) Membership in a vulnerable population (e.g., pregnant women) (medical record or self-report), 5) History of significant violence towards VA staff (medical record), 6) Participation in another psychotherapy research study, (medical record

or self-report), and 7) Current participation in an EBP for a condition related to moral injury (medical record or self-report).

C. Study Design and Research Methods

Design: We are proposing a two arm, randomized, controlled pilot study to assess the feasibility of a future randomized clinical trial (RCT) evaluating the efficacy of ACT-MI. Candidate measures for a future efficacy trial will be administered at baseline, post-treatment, and one- and three-month follow-ups. Measures of acceptability will be administered following treatment completion/discontinuation. Veterans who are eligible to receive treatment at the VA ECHCS and who are eligible and interested in participating in the study will be enrolled and randomized to: (1) Present Centered Therapy (PCT-MI) or (2) ACT-MI.

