Preliminary Screening. Preliminary screening will occur in person or by telephone. After detailed information about the study is shared, potential participants will be given the option to provide verbal consent and complete a verbal screening interview based on inclusion and exclusion criteria. Research personnel will also review the Veteran's medical records to further evaluate study eligibility. Following the screening, potential participants will be scheduled for their Baseline Assessment. Their appointment may also be confirmed via text message. ***Baseline Assessment Session and Randomization.*** Baseline assessment sessions will be conducted in person when possible. When necessary, baseline sessions will be conducted online using REDCap and telephone/videoconferencing. A waiver of consent and HIPAA are being requested to allow for a consent process with a postcard consent rather than a formal physical signed consent form. After demonstrating understanding of the postcard consent and indicating willingness to participate, participants will complete the safety measure (UWRAP) and then assessment measures (SCID-5 modules, C-SSRS, VLQ, PROMIS, OQ-45, PHLMS, AAQ-II, AAQ-II past week MEAQ-30, MEAQ-30 past week, CFQ-MI, CFQ-MI past week, PHLMS, PHQ-9, PCL-5, E-MIS, AUDIT, BAM-R and ASIQ). Participants and the study assessor will be blind to condition. At the conclusion of the assessment session, participants will be randomized to ACT-MI or PCT-MI. The study biostatistician will predetermine group assignment through block randomization to ACT-MI or PCT-MI (block size = 4); stratified to condition based on previous participation in an Evidence-Based Psychotherapy (EBP). We chose to stratify participants based on past EBP participation as we believe previous treatment engagement could significantly impact responsiveness to treatment and thus want to ensure that the groups are as evenly distributed as possible based on this variable. We felt this was more important to prioritize than stratifying for diagnosis given the transdiagnostic nature of the proposed intervention. Randomization results will be concealed in a sealed envelope until the end of the baseline assessment session. ***Treatment Participation.*** Participants randomized to either ACT-MI or PCT-MI will complete the intervention in an outpatient context. When necessary, ACT-MI and PCT-MI will be conducted over a VA approved videoconferencing platform. The treatments will be delivered across twelve group sessions. Investigators will attempt to offer treatment as quickly as possible, however, this will be dependent on group start dates. Participants will

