
receive up to eighteen hours of group psychotherapy across twelve group sessions. Prior to each treatment group, participants will complete process measures (PHLMS, AAQ-II, MEAQ-30 and CFQ-MI). On odd weeks participants will complete the AAQ-II and PHLMS and on even weeks participants will complete the MEAQ-30 and CFQ-MI. These will be assigned on odd and even weeks to minimize participant fatigue and to determine which measures might be most sensitive to change over time for use in a future efficacy trial. Groups will be randomly assigned to receive either the original measures or the measures with altered instructions (e.g., to identify experiences in the past week) so that we can better understand responding on these measures based on providing temporal instructions. At baseline and post-treatment for 7 days, 3 times per day, participants will complete EMA assessments. EMA will be structured to minimize its impact as a potential treatment procedure and instead will be explicitly designed to assess behavioral changes without necessarily prompting values driven behavior. ***Post-treatment Assessment***

Session. A study assessor will meet with participants in the ACT-MI and PCT-MI conditions and administer the treatment acceptability measures (CSQ-8, NEII, RT-C) and candidate outcome measures (VLQ, PROMIS, OQ-45, PHLMS, AAQ-II, AAQ-II past week MEAQ-30, MEAQ-30 past week, CFQ-MI, CFQ-MI past week, PHQ-9, PCL-5, E-MIS, AUDIT, BAM-R, ASIQ, and GC). **One-Month and Three-Month Follow-ups.** Participants will have the option to complete follow-up assessments via survey link (i.e., REDCap), mail, or phone/videoconferencing. In person follow-up appointments may still be offered, dependent on contact restrictions and recommendations related to the COVID pandemic. A different assessor, still blind to condition, will administer the one- and three-month follow-up measures (VLQ, PROMIS, OQ-45, PHLMS, AAQ-II, AAQ-II past week MEAQ-30, MEAQ-30 past week, CFQ-MI, CFQ-MI past week, PHQ-9, PCL-5, E-MIS, AUDIT, BAM-R, ASIQ, GC, and CSQ).

Recruitment:

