- 7) *What are the benefits of participating in this study?*

Veterans who cannot adequately answer these questions will be excluded from participating.

Participants will have had the option during the screening and verbal consent to receive text message PHI/PII-free text message reminders for their baseline appointment. During the baseline appointment consent process, participants will select their reminder and scheduling preferences for the one- and three-month follow-up appointments. Participants will receive reminder phone calls and letters. They will select the level of detail that can be used for the reminder phone calls (please see consent form for details). As in COMIRB #15-0346, #16-0350, and #17-0603 participants will also be given the option of receiving text message reminders stating "REMINDER: You have a research appointment on [month, day, year] at [time]. Please call [contact phone number] if you have any questions." If the study team has been unable to reach a participant to schedule or reschedule a follow-up appointment, the participant will be sent a text message stating "REMINDER: Please contact our research coordinator to schedule your appointment [contact phone number]." Text messages will not contain PII or PHI.

Protected Health Information (PHI). PHI to be collected may include: first and last name, date of birth, mailing address, and full social security number. This information is needed to access participants' medical records to collect data for this study. Additional PHI will include demographic information (including military history), use of VA services, and medical and mental health history.

Authorization Procedures. A waiver of consent and a HIPAA Waiver of Authorization is being requested for the entire study. This will allow members of the research team to view medical charts of potentially eligible patients. The medical records will be reviewed to screen potential participants to determine study eligibility and appropriateness to participate in the intervention. Review of the medical records also allows members of the research team to screen for other criteria that would exclude participation (e.g., safety-related issues, psychiatric distress) and reduce burden on ineligible patients. The consent and HIPAA waiver will also allow study participants to complete the study online when face-to-face sessions are not able to be offered.

V. Description, Risks and Justification of Procedures and Data Collection Tools:

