acceptability and feasibility summary statistics. Results will be presented across participants and individually for each group. **Sample Size.** Areán and Kraemer recommend sample sizes between 50 and 100 to generate variability estimates for outcome measures and to facilitate a “dress rehearsal for the clinical trial” (p. 95).¹⁷ As this trial serves as a precursor to a larger scale efficacy study and one of our goals is to determine the fit of candidate outcome measures, we will enroll 36 participants per condition (72 participants total) to account for attrition. As a method of data analysis for qualitative measures, thematic content analysis will be used as an iterative process of interpretation for the purposes of scoring, coding, and seeking patterns (themes) across verbal materials so that inferences about characteristics of a group can be generated.^{97, 5} First, data will be recorded and coded without identifiers. Reviewers will independently code interviews. Each interview will be coded by at least two reviewers. Reviewers will independently identify themes among codes. Reliability and validity among themes between reviewers will be determined in a consensus meeting. In the consensus meeting the coding team will define and name the themes that best represent the narratives from the individual interviews. This process is consistent with previous qualitative research conducted on moral injury.⁵

Aim 1: Evaluate the acceptability of the ACT-MI intervention for Veterans experiencing impairment in functioning associated with moral injury. We will assess the proportion of participants who find ACT-MI acceptable, defined as $\geq 70\%$ of participants scoring ≥ 24 on the Client Satisfaction Questionnaire (CSQ).¹⁹ The Narrative Evaluation of Intervention Interview (NEII)²⁰ will be used to inform any necessary revisions to the intervention and refinement of the treatment manual. Qualitative data collected using the NEII will be used to understand the limitations and strengths of the interventions via thematic content analysis. If fewer than 70% of participants find ACT-MI or PCT-MI acceptable, the qualitative data will be examined to determine areas for improvement.²⁰

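### A fixed, printed block size of 4 lets anyone who knows a stratum's past assignments deduce up to a third of allocations, and the protocol does not say who knows them

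*Combined protocol and SAP*

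**What the plan says.** Section IV.C, Baseline Assessment Session and Randomization, states that "The study biostatistician will predetermine group assignment" and that this is done "through block randomization to ACT-MI or PCT-MI (block size = 4); stratified to condition based on previous participation" in an EBP. On concealment it says: "Randomization results will be concealed in a sealed envelope until the end of the baseline assessment session". The same paragraph says "Participants and the study assessor will be blind to condition", and the paragraph on follow-ups adds "A different assessor, still blind to condition, will administer the one- and three-month follow-up measures".

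Section VII, Sample Size, gives the numbers: "we will enroll 36 participants per condition (72 participants total) to account for attrition".

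Two places show judgement entering eligibility before the envelope is opened:

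- Exclusion criterion 2 in Section IV.B (inability to complete the study measures) may be decided on "results of veteran self-report, screening, or discretion of interviewer".
- Section IV.C, Morally Injurious Event Screeners, uses a semi-structured interview to judge functional impairment and moral pain, which bear on inclusion criterion 4.

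The protocol does not say who holds or opens the envelopes, whether the staff who screen and book participants can see past assignments, or whether the block size is withheld from them.

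**The concern.** A sealed envelope protects one assignment at a time. When blocks have a known, constant size, past assignments in a stratum reveal some of the later ones, whatever the envelope hides. The block size is printed in the protocol. The stratum can be learned during screening, because the medical record is reviewed then. Past assignments could become known once participants join ACT-MI or PCT-MI groups, since therapists and group members will know which treatment is being given.

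If a person who judges eligibility also had that information, a Veteran thought to suit one treatment could, even without intent, be more or less likely to enter at a foreseeable place. The figures exposed are those reported by arm: the share with a CSQ score of at least 24 (criterion at least 70%), treatment completion, and loss to follow-up (criterion at most 30%). No later analysis repairs selection at entry. The study is also described as a rehearsal for an efficacy trial, where the same allocation method would matter more.

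**Working it through.** The plan gives no predictability figure, so there is none to reproduce. Its sample-size arithmetic is consistent: 36 × 2 = 72, which is 18 blocks of 4.

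**Inputs.** Block size 4 and two strata, prior EBP yes or no (Section IV.C). Allocation 1:1, so two of each arm per block (from 36 per condition, Section VII). The share of participants with prior EBP is not given; 25% and 50% are assumed below.

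**Step 1: upper bound, by enumeration.** A block of 4 has 6 equally likely sequences, or 24 places. A place is certain when one arm is already used up. The observer knows the block size, the stratum and all past assignments in it.

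| Place in block | Chance it is certain | Best-guess success |
|---|---|---|
| 1 | 0 | 1/2 |
| 2 | 0 | 2/3 |
| 3 | 1/3 | 2/3 |
| 4 | 1 | 1 |

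Certain: (0 + 0 + 1/3 + 1)/4 = 1/3, that is 8 of 24 places, or 18 × 4/3 = 24 of 72. Best guess: (1/2 + 2/3 + 2/3 + 1)/4 = 17/24 = 70.8%.

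**Step 2: incomplete last blocks.** In simulation with 72 participants in two strata, about 32% of allocations are certain (about 23 of 72; 95% of runs between 19 and 27) and the best guess is about 70%. The result is the same for both assumed EBP shares.

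**Step 3: participants pending.** The envelope is opened only at the end of the baseline session. Suppose one person in the same stratum is booked but not yet randomized when the next person is considered. The immediately preceding assignment is then unknown. Place 3 is never certain, and place 4 is certain only if places 1 and 2 went to the same arm, with chance 1/3. Certain: (1/3)/4 = 1/12 = 8.3%, that is 2 of 24 places, or 18 × 1/3 = 6 of 72. With two pending, only place 1 is known when place 4 is considered, so nothing is certain: 0%.

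**Step 4: stratum unknown.** If the observer does not know each participant's stratum, simulation gives about 2% certain and a best guess of about 65%.

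**Step 5: the alternative.** Block sizes of 4, 6 and 8 are chosen at random. The observer guesses optimally and knows the set of sizes but not the size of each block. Certain allocations fall to 2.3% to 2.5% across the runs (about 2 of 72), and the best guess to 67.4% to 67.6%. The gain is the near-loss of certainty; the guess rate falls by only about 3 points.

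**Step 6: price in balance.** The largest imbalance in an unfinished block is half its size: 2 for a block of 4, and 4 for a block of 8. Over two strata the worst case goes from 4 to 8 of 72.

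**The case against.** The strongest reply is that the key condition is not in the documents. A reader might infer that the trial is open-label and that enrolling staff therefore know the past assignments. The protocol never uses that term. It describes participants and the assessor as blind at baseline and names a different blinded assessor for follow-up. Therapists and group members must come to know the treatment, but that does not show that screeners do. This part of the reply stands: staff knowledge is a possibility left open, not a fact.

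A reader might also infer that screening and scheduling are at staff discretion. The text does not go that far. Interviewer discretion is written into one exclusion criterion, and most others rest on the medical record or self-report. The phrase "determine study eligibility and appropriateness to participate in the intervention" in Authorization Procedures explains why charts are reviewed under the waiver; it does not add an eligibility step based on fit with ACT-MI. No text gives staff freedom over the order of baseline visits. What remains is the one exclusion criterion and the semi-structured interview.

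Third, the pilot is descriptive and by intent not powered for efficacy. The variability estimates for the future sample size are taken across groups, and fidelity is reported by clinician, so neither depends heavily on who enters which arm. This limits the consequence but does not remove it for the per-arm acceptability and retention figures.

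None of this answers the narrower point. The envelope does not prevent deduction from past assignments, and the block size is constant and printed.

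**Conclusion.** The concern holds as a cheap improvement. Up to one third of allocations could be deduced with certainty by someone who knows the block size, the stratum and the full history in that stratum. The realistic share may be far lower: about 8% with one same-stratum participant pending, none with two, and about 2% if the stratum is unknown. The documents do not give the number pending.

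The stronger reading, that enrolling staff do foresee a third of assignments and that selection would distort the results, is not supported. The documents are silent on who sees past assignments, and nothing in them allows the size of any shift in the CSQ, completion or follow-up figures to be estimated. The supportable statement is that selection could affect those per-arm figures, and that the protocol leaves this open when it could readily close it.

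**What to change.** For any allocations still to be made, and for the efficacy trial, have the study biostatistician generate the list with block sizes varying at random (for example 4, 6 and 8) within the same prior-EBP strata. Keep the sizes out of documents that enrolling staff see, and hold them with the biostatistician until enrolment ends. Add a sentence saying who holds and opens the envelopes and whether screening staff can see past assignments.

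The cost is a new list for the remaining envelopes and a short protocol edit. The larger possible imbalance may make the two sets of therapy groups fill slightly less evenly. The version is dated 12/12/2022 and does not give enrolment status. If enrolment is complete, report the fixed block size as a limitation and change the method for the efficacy trial.

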Aim 3 Measures: Select measures and calculate necessary sample size for a future efficacy study. The following measures will be included as candidate outcome measures for a future efficacy trial, and be administered at baseline, post-treatment, one-month, and three-month assessment sessions. Candidate measures will include assessments of three domains.

Baseline measures to diagnostically characterize the sample: To characterize the sample at baseline the Structured Clinical Interview for the DSM-5, the Columbia-Suicide

Severity Rating Scale, and the Moral Injury Outcome Scale will be administered.

Structured Clinical Interview for DSM 5 Research Version (SCID-5-RV)- Modules A, D, E, F, and L is a diagnostic interview used to determine DSM-5 disorders. All participants will be administered the SCID-5-RV during the baseline assessment session. Specifically we will administer the following modules: A- Mood Episodes, D- Differential Diagnosis of Mood Disorders, E- Substance Use Disorders, F- Anxiety Disorders, and L- Trauma- and Stressor-related Disorders. This will provide a broader diagnostic characterization of the participants. *Approximate time to complete: 30 minutes.* **The Columbia-Suicide Severity Rating Scale (C-SSRS)** (Posner, Brown, Stanley, Brent, Yershova, Oquendo, Currier, Melvin, Greenhill, Shen, & Mann 2011): The C-SSRS is a clinician-administered measure that assesses for suicidal ideation and attempt behavior based on established definitions. The C-SSRS assesses intensity of suicidal ideation, specifically asking about frequency, duration, intrusiveness, controllability, and deterrents, as well as suicide-related behavior, such as actual attempts and aborted attempts.

Approximate time to complete: 10 minutes. **Moral Injury Outcome Scale (MIOS)** (Lits, Phelps, Frankfurt, Murphy, Nazarov, Houle, Levi-Belz, Zerach, Dell, Hosseiny & members of the *Moral Injury Outcome Scale Consortium* 2021): The MIOS is a 32-item self-report measure used to assess the type of morally injurious event experienced, as well as the extent to which that event has affected functioning. The MIOS assesses the impact a morally injurious event has had on trust, guilt, self-doubt, and faith in relation to the self, others, and spiritual practices. *Approximate time to complete: 10 minutes.*

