All participants will be provided with ample time to ask questions prior to enrolling in the study. As noted above, a series of questions will assess participants' understanding of the study in order to ensure that participants have adequately comprehended the critical information (e.g., risks/benefits, voluntary nature) and are able to complete the consent process. Participants will be clearly informed that the study is voluntary and that they can withdraw from the study at any time, with no penalty. Additionally, all research staff have been trained in human subjects research. The main risk to participating in the study is potential emotional discomfort during the assessments. ACT-MI and PCT-MI participation may also be associated with some emotional discomfort, but this is not anticipated to be any more severe than the emotional discomfort associated with psychotherapy used in standard care.

Adverse events

Significant adverse events are not expected. For the purposes of this study, adverse events are defined as any newly identified medical diagnoses noted by medical personnel, or symptoms reported by the participant, which are *directly related to participation in the study and occur during the administration of testing/treatment or appear within two weeks of testing/treatment*. Participants will be instructed to contact the principal investigator if they believe they have potentially experienced an adverse event. Any adverse event will be reported to COMIRB by the PI in keeping with COMIRB regulations.

Risks

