As noted above, adverse events are not expected. The anticipated risks and discomfort associated with research procedures are not greater than those that would be ordinarily encountered during routine clinical care or psychological assessment, in which discussion of mental health and past traumatic events is the standard of care. Participants are at elevated risk for emotional distress and related sequelae by virtue of the fact that they have moral injury. For participants who reveal any imminent suicidality during the baseline assessment, or active suicidal ideation during the follow-up visits, the appropriate follow-up actions will be implemented by Drs. [name], [name], or other designated clinician with expertise in suicide risk assessment. Please see "Safety Monitoring" section below for more details. Participants also have the potential to become frustrated, fatigued, or distressed while completing study measures. Members of the research team will be trained to minimize psychological distress while assisting individuals in completing the protocol.

There is a potential loss of confidentiality and/or privacy. Minimizing risks to data security will be achieved by employing safeguards built into the framework of the VA Office of Research and Development (R&D).

Benefits

The primary benefit of this study is generalizable knowledge to help better understand the acceptability and feasibility of ACT for Moral Injury. Although ACT for Moral Injury is empirically informed, its efficacy has not been evaluated; therefore, no direct benefits to the

participants can necessarily be anticipated. Similarly, PCT-MI has not been used in a group format for moral injury and has not had its efficacy evaluated; therefore, direct benefits for participants in PCT-MI can not necessarily be anticipated.

Safety Monitoring

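### Direct relatedness and a two-week window decide whether an adverse event counts at all, so a comparison of events between arms would be incomplete and open to bias

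*Combined protocol and SAP*

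**What the plan says.** Section V (Adverse events) defines an adverse event, for this study, as a new diagnosis noted by medical staff or a symptom the participant reports that is "directly related to participation in the study and occur during the administration of testing/treatment or appear within two weeks of testing/treatment". The causal and timing conditions are joined, so both must be met.

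On detection, the same section says: "Participants will be instructed to contact the principal investigator if they believe they have potentially experienced an adverse event". Safety Monitoring adds that participants receive contact details for making such reports. No scheduled adverse event question or form appears. On reporting: "Any adverse event will be reported to COMIRB by the PI in keeping with COMIRB regulations".

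Section V (Risks) says of the population: "Participants are at elevated risk for emotional distress and related sequelae by virtue of the fact that they have moral injury".

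The Data Analysis Plan (section VII) is descriptive. It covers acceptability, feasibility and the candidate measures, with means, standard deviations and confidence intervals within and across groups. It contains no adverse event summary.

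**The concern.** Relatedness is usually recorded about an event after the event has been captured. Here an event judged unrelated never becomes an adverse event, so the judgement cannot be checked later and the arms cannot be compared on all events. The two-week limit removes further events by date. Relying on participants to make contact removes those that nobody reports.

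Suicide attempts, psychiatric admissions and deaths matter most here, and the definition names none of them. Recruitment mailings may go to Veterans with a history of suicidal behaviour, and section V (Benefits) says that neither treatment's efficacy has been evaluated. The pilot is meant to rehearse the efficacy trial. A low count under this rule would partly reflect the rule, and the later trial would inherit untested procedures for collecting harms.

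**Working it through.** The plan gives no figure for this point, so there is none to reproduce. The check has three parts.

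**1. Relatedness condition.** The causal and timing conditions are joined by *and*, so the causal filter applies on every day of the study, including days inside the window. Section IV.C (Procedures) blinds the assessors at baseline and follow-up. No section says who judges relatedness.

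**2. Time window.** Inputs:
- Assessments: candidate measures are to "be administered at baseline, post-treatment, one-month, and three-month assessment sessions" (IV.A, Aim 3 Measures). Each visit is testing and opens its own window.
- Treatment: "The treatments will be delivered across twelve group sessions" (IV.C). Weekly spacing is inferred from "On odd weeks participants will complete the AAQ-II and PHLMS and on even weeks participants will complete the MEAQ-30 and CFQ-MI".
- EMA: "At baseline and post-treatment for 7 days, 3 times per day, participants will complete EMA assessments" (IV.C). It may or may not count as testing.
- Assumptions: day 0 is the last session; the one-month visit is on day 28 or 30 and the three-month visit on day 84 or 91; all visits are attended.

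*Treatment phase.* Sessions 7 days apart with 14-day windows leave no gap, so every day from session 1 to 14 days after the last session is inside. The wait between baseline and session 1 is not counted, because the document gives no length for it.

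*Post-treatment follow-up.* Share outside = 1 − (days covered ÷ days of follow-up).

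| Reading | Days covered | Outside, 84 days | Outside, 91 days |
|---|---|---|---|
| Forward; post-treatment visit on day 0 | 14 + 14 = 28 | 1 − 28/84 = 67% | 1 − 28/91 = 69% |
| Forward; post-treatment visit on day 7 | 21 + 14 = 35 | 1 − 35/84 = 58% | 1 − 35/91 = 62% |
| As above, EMA week (days 7–14) counts as testing | 28 + 14 = 42 | 1 − 42/84 = 50% | 1 − 42/91 = 54% |
| Two weeks before or after; post-treatment visit on day 0 | 14 + 28 + 14 = 56 | 1 − 56/84 = 33% | 1 − 56/91 = 38% |

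From session 1 to the three-month visit, with the post-treatment visit on day 0 and forward windows, coverage is 77 + 28 = 105 days out of 77 + 84 = 161 (65%) or 77 + 91 = 168 (63%).

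**3. Whether other instruments fill the gap.**
- C-SSRS: covers suicide attempts, but is given at baseline only.
- UWRAP: given at all assessments, with debriefing after assessment or treatment sessions. Its suicide items ask about urge and intent at that moment (Appendix 1), not about the interval since the last visit.
- ASIQ: suicidal ideation, at all four time points.
- PHQ-9 and PCL-5: symptom scores, at all four time points.
- GC: self-rated change, including worsening, at the three later time points.

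None of the repeated instruments is described as recording attempts, admissions or deaths between visits. Follow-up may also be completed by survey link or mail (IV.C), where there may be no conversation in which an event could come up.

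**What a comparison could show.** With n = 36 per arm and a two-sided 5% test, power = Φ{[Δ − 1.96√(2p̄(1−p̄)/n)] ÷ √([p₁(1−p₁)+p₂(1−p₂)]/n)}. For assumed event rates of 10% against 25%, 30% and 40%, this gives 39%, 57% and 85%. Any comparison of events would be descriptive, even with complete capture.

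**The case against.** The strongest reply is that this is a feasibility pilot with no safety aim, and that safety monitoring is active. The UWRAP is scheduled and sends raised scores to a clinician. Five symptom and risk scales (ASIQ, PHQ-9, PCL-5, AUDIT, BAM-R) are given at all four time points in both arms, and the GC runs down to a great deal worse. The definition and the visit schedule are the same in both arms, and candidate measures will be summarised by group. All of this stands. It lowers the weight of the point, but it does not supply a record of attempts, admissions or deaths between visits.

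A reader might infer four stronger things that the documents do not support:
- *That harms cannot be compared between arms.* Recorded events can be tabulated by arm, and the symptom scales give a second comparison.
- *That relatedness is judged by someone who knows the arm.* The document is silent on this.
- *That 69% of follow-up is outside the definition.* That is the upper end of a range that depends on visit timing, on whether EMA is testing, and on how the window is read.
- *That an event six weeks after the last session is excluded by its date.* Day 42 lies inside the two weeks after a one-month visit on day 28 or 30. If that visit took place, only the relatedness condition could exclude the event.

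**Conclusion.** The concern holds in a limited form. The relatedness condition is the firmer part: it follows from the text, needs no timing assumption and applies throughout. The time window adds to it after treatment only. Between about one third and 69% of the follow-up to three months is outside, and 50–69% on the forward readings. These figures assume weekly sessions, 84–91 days of follow-up and attended visits.

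With reporting left to participants and no summary by arm planned, a comparison of adverse events as defined would be incomplete and open to bias, though not impossible. The acceptability and feasibility aims are not threatened. The change is worth making because the population is at elevated risk and the pilot prepares the efficacy trial.

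**What to change.** - Record every untoward event from consent to the three-month visit, regardless of relatedness. Name suicide attempts, psychiatric admissions and deaths.
- Add one scripted item to each existing assessment, including the survey and mail versions.
- Add a check of the medical records, which the team already has access to (section IV, Enrollment), for deaths and for participants lost to follow-up. A visit question cannot find these, and up to 30% loss is treated as feasible.
- Record relatedness as a separate attribute, and state who assigns it and whether that person is blind.
- Add to section VII a descriptive table by arm of all events and of related events.
- Leave reporting to the board as the protocol states it.

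The cost is a little more data collection: one item per assessment, a record check and one table. Reported event counts will be higher. The record check finds only what reaches those records.
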